7.8.10.2. Safety Endpoints

All-cause in-hospital death without any restriction will replace in-hospital cardiovascular death as the sensitivity analysis on secondary safety endpoints.

The cardiovascular events (MI, stroke, and heart failure) in the secondary endpoint is the first post-index incidence recorded on a hospital claim or physician claim. To evaluate possible overestimation, new incident of MI, stroke, or heart failure as no previous diagnosis in the 183 days preceding the index date as in the Sentinel Initiative ([Cutrona et al, 2013](#)) will be carried as a sensitivity analysis.

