Comparative cardiovascular safety for PS-matched ABL-treated patients versus TPTD-treated patients will be evaluated based on time to the first incidence of the composite endpoint of nonfatal myocardial infarction (MI), nonfatal stroke, and in-hospital cardiovascular death within the 18 months after treatment initiation while still on therapy. The International Classification of Diseases, 10th Revision, Clinical modification (ICD-10-CM) codes for MI, stroke, and heart failure from the Food and Drug Administration (FDA) Mini-Sentinel database ([FDA, 2021](#)) will be used as a guide for event identification with modifications to ensure that relevant endpoints are captured ([Appendix 4](#)). Published results from a validation study of the MI codes used in the Mini-Sentinel database demonstrated a positive predictive value of 86% ([Cutrona et al, 2013](#)). For evaluation of mortality, hospital discharge status will be used. It is important to note that hospital claims do not specify the cause of death nor causal association with a specific medication. A previously validated claims-based algorithm will be used to derive in-hospital cardiovascular death (indirect approach 2, [Xie et al, 2018](#)). Compared to a previously published fatal MI and stroke method ([Ritchey et al, 2017](#)), the algorithm we adopted has higher sensitivity while maintaining high specificity. The net reclassification index is improved.

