7.8.7. Safety Analyses

A Cox proportional hazards model will be used for the time to first cardiovascular event. HR and 95% CIs will be presented.

The ICD-10 diagnosis from the hospital claim and physician claim will be used to derive post-index myocardial infarction (MI) (I21.x, I22.x), stroke (I61.x – I63.x), or heart failure (I50.x, excluding I50.x2, I50.8x). Hospital discharge status code (20 to 29 or 40 to 42) will be derived for in-hospital death. A detailed code list is provided in [Appendix 3](#). Subjects with in-hospital cardiovascular death derived from indirect approach 2 ([Xie et al, 2018](#)) will be included in the analyses. 2018 ICD-10 CM and General Equivalence Mappings (GEMS) from the Centers for Medicare & Medicaid (CMS) ([will be used to translating ICD-9 CM to ICD-10 CM \(CMS, 2018\)](#)).

The As-Treated (AT) analysis will be conducted for the safety evaluation. The first incidence of a cardiovascular event after the index date and before the 30 days after the end of treatment will be analyzed.

A cardiovascular event is the first incidence of the composite endpoint of nonfatal MI, nonfatal stroke, or in-hospital cardiovascular death; the first incidence of the composite incidence of nonfatal MI, nonfatal stroke, heart failure or in-hospital cardiovascular death; or the first incidence of MI, stroke, heart failure, or in-hospital cardiovascular death separately.

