7.8.11. Subgroup Analyses

The absence of BMD data is a limitation of the study because BMD is often used for risk assessment. Instead, we propose to evaluate patients based on previous fracture history, which is the greatest predictor of future fracture risk ([Banefelt et al, 2019](#); [Balasubramanian et al, 2019](#)).

We propose to have a subgroup analysis of patients with previous bisphosphonate use. Most (64.7%) of patients in the EU had previously used bisphosphonates ([Langdahl et al, 2018](#)). Additional subgroup analyses include evaluation of outcomes by age group and by race/ethnicity.

7.8.11.1. Subgroup Analyses for Effectiveness:

The following subgroup analyses will be performed:

- Age group: < 75 years vs. \geq 75 years
- Race/ethnicity: White, Hispanic, African American, Asian, Other, Unknown, Missing
- Prior use of bisphosphonates within 5 years before the index date: with vs. without
- Prior fracture within 1 year before the index date: with vs. without

Each subgroup will be PS-matched separately to ensure the comparability between the patients in the ABL and TPTD groups.

7.8.11.2. Subgroup Analyses for Safety:

Subgroup analyses will be performed by:

- Age group (age < 75 years vs. age \geq 75 years)
- Race/ethnicity: White, Hispanic, African American, Asian, Other, Unknown, Missing
- With or without prior cardiovascular risk
- With or without MI or stroke within 1 year before the index date.

Each subgroup will be PS-matched separately to ensure the comparability between ABL and TPTD.

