9. MANAGEMENT AND REPORTING OF ADVERSE EVENTS/ADVERSE REACTIONS

The design of this study is characterized by secondary use of data previously collected from health insurance claims. Thus, for this study the submission of suspected adverse reactions in the form of Individual Case Safety Reports (ICSRs) is not required. The study design was retrospective and there were no claims adjudication. No validated algorithm was used to confirm events were incident events. Claims are therefore only “proxies” for events.

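### The main cardiovascular event definition has no look-back, so repeat claims for pre-index MI, stroke or heart failure can be scored as on-treatment first events

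*Combined protocol and SAP*

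**What the plan says.** Both secondary endpoints (Section 5.2) are time-to-first-event composites, with and without heart failure, assessed on treatment. Three places define how a component is scored.

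- Section 7.8.7 names the source: "The ICD-10 diagnosis from the hospital claim and physician claim will be used to derive post-index myocardial infarction (MI"), followed by the stroke and heart failure codes. MI is I21.x or I22.x, stroke is I61.x to I63.x, and the last group is "heart failure (I50.x, excluding I50.x2, I50.8x"). The analysis window runs from index to 30 days after the end of treatment.
- Section 7.8.10.2 confirms the main rule: the event "is the first post-index incidence recorded on a hospital claim or physician claim".
- The same section adds a sensitivity analysis, introduced with "To evaluate possible overestimation", which counts "new incident of MI, stroke, or heart failure as no previous diagnosis in the 183 days preceding the index date".

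Prior MI, stroke and heart failure are extracted as history (Section 7.6.2) but are not among the exclusions in Table 2. Section 7.8.11.2 expects such women, because one safety subgroup is "With or without MI or stroke within 1 year before the index date". Section 9 states: "No validated algorithm was used to confirm events were incident events".

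**The concern.** The earliest billing record of a condition after index is not the same as its first occurrence after index. A woman with known heart failure who is billed under a listed I50 code at a routine visit meets the main definition. So does a woman admitted with MI shortly before her first fill whose physician follow-up is billed under I21.x. Those two routes are where carry-over is most plausible.

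A carry-over claim does harm twice. It adds an event that arose before treatment. And because only the first event counts, it ends follow-up for that composite, so a later true event in the same woman is lost.

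The fracture endpoint is treated differently. Appendix 2 reads fracture claims from 5 years before index and lets an episode at one site run until there is a 90-day gap between claims. The visible text has no comparable rule for the cardiovascular components. Section 6.3 describes the study as reasonably powered to show that the two drugs are comparable in safety. If carry-over is similar in both cohorts, it works in favour of that conclusion.

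**Working it through.** **No plan figure to reproduce.** The documents state no event rate, event count, margin or power for the safety endpoints, and no carry-over rate. The size below is therefore an illustration over assumed ranges.

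**Formula.** Let f be the share of counted teriparatide events that are carry-over, and r the abaloparatide-to-teriparatide ratio of carry-over rates. With rare events and cohorts of equal size, per counted teriparatide event there are (1 − f) true events and f carry-over events. The abaloparatide cohort then has HR × (1 − f) true events and r × f carry-over events. So

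HR observed = HR true × (1 − f) + r × f.

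**Equal carry-over (r = 1; f assumed).**

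| True HR | f = 10% | f = 25% | f = 50% |
|---|---|---|---|
| 0.7 | 0.73 | 0.775 | 0.85 |
| 1.3 | 1.27 | 1.225 | 1.15 |
| 1.5 | 1.45 | 1.375 | 1.25 |
| 2.0 | 1.90 | 1.75 | 1.50 |

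For example, 1.5 × 0.5 + 1 × 0.5 = 1.25. Every entry moves toward 1.

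**Cross-check.** A simulation took a 0.6% true event risk in the reference cohort and a 50% chance that a prevalent case is billed again. It used a person-time rate ratio, not a fitted Cox model. For a true HR of 1.5 it gave 1.46, 1.36 and 1.26 at f = 14.3%, 25.3% and 49.1%. The formula gives 1.43, 1.37 and 1.25. These agree within simulation error.

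**Unequal carry-over.** With a true HR of 1.0 and f from 10% to 50%, r = 0.8 gives 0.98 to 0.90, and r = 1.25 gives 1.025 to 1.125. The direction is then no longer fixed.

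**Scale against random error.** Section 6.2.3 reports MACE in 0.5% of abaloparatide and 0.6% of teriparatide participants in the earlier trial. With 8,000 per cohort (Section 7.8.1.2) that is 8,000 × (0.005 + 0.006) = 88 events. The 95% CI then runs from HR/1.52 to HR × 1.52, since exp(1.96 × 2/√88) = 1.52. The shift from 1.5 to 1.25 is a factor of 1.20, so it lies inside that interval. But carry-over also adds events. If half of all counted events were carry-over, 88 true events would become 176 counted, and the factor would fall to exp(3.92/√176) = 1.34. The interval would look tighter around a value nearer 1. The trial proportions serve only for scale, because the claims population and the as-treated window differ.

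**The case against.** The plan is open about the problem. It names overestimation, prespecifies the 183-day analysis, plans subgroups by prior cardiovascular risk and by recent MI or stroke, and says that incident status is not confirmed. Both hazard ratios will be reported, and safety has no margin that a diluted HR could pass. An inclusive main definition also keeps true recurrences, which matter when perhaps 88 MACE events are expected. All of this is fair and lowers the stakes. It does not explain why the headline estimate of a first-event endpoint should rest on the definition that the plan itself suspects, and the plan does not say how to read a disagreement between the two.

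Four stronger readings are tempting, and the documents do not support them.

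- *The HR is necessarily pulled toward 1.* That needs similar carry-over in both cohorts. Section 7.8.5 names age, fracture history, osteoporosis-related hospitalization and fall-risk comorbidities and medications. Section 7.6.3 places prior stroke among the fall-risk conditions but cardiovascular disease elsewhere. The Appendix 1 list is not visible, so balance on prior MI and heart failure cannot be confirmed. Billing might also depend on the drug: Section 6.2.3 reports a larger heart-rate rise with abaloparatide (7.9 against 5.3 bpm), which could prompt visits at which known disease is coded. That is a possibility, not a documented fact.
- *Any claim counts.* Only listed codes count, some I50 codes are removed, and the detail of Appendix 3 is not visible.
- *The MI validation figure in Section 5.3 ("demonstrated a positive predictive value of 86"%) holds only under the 183-day rule.* The plan cites one study for both, but does not say that the figure was estimated under that rule.
- *The trial's 1.0% and 1.7% can serve as reference-arm MACE rates.* In Section 6.2.3 only 0.6% is a teriparatide MACE proportion. The 1.7% is placebo MACE plus heart failure, and the 1.0% appears only for serious cardiac adverse events.

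**Conclusion.** The point holds, with a conditional direction. The main definition has no look-back, accepts physician claims and applies to a cohort that includes women with prior disease, so it can count pre-index disease as on-treatment events. The plan's own remedy sits only in a sensitivity analysis. With equal carry-over making up 10% to 50% of counted teriparatide events, a true HR of 1.5 would read 1.45 to 1.25. Both the range and the equality are assumptions. With unequal carry-over the HR can move either way, so no correction factor can be given in advance. This is a weakness of the headline safety estimate that should be repaired. It is partly mitigated by the planned sensitivity analysis and does not invalidate the study.

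**What to change.** In Sections 7.8.7 and 7.8.10.2, exchange the two definitions.

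- **Main analysis:** for both composites and for the single MI, stroke and heart failure endpoints, count a component only if it has no diagnosis claim in the 183 days before index. State that the rule is applied component by component, so that a woman with a prior diagnosis of one component stays at risk for the others.
- **Sensitivity analysis:** keep the present definition, the first post-index claim with a listed code.

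**Cost.** This is mainly SAP wording, since both definitions are already specified for the secondary endpoints and no new data are needed. True recurrences in women with the same diagnosis in the prior 183 days leave the main analysis, so there are fewer events and a somewhat wider CI. For scale, if 10% of 88 events were lost in this way (an assumption), about 79 would remain and the CI factor would go from 1.52 to exp(3.92/√79) = 1.55. The loss would be proportionately larger in the subgroup with MI or stroke in the prior year. The window is also partial: a diagnosis older than 183 days can still carry over, and the report should say so.

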7.8.11. Subgroup Analyses

The absence of BMD data is a limitation of the study because BMD is often used for risk assessment. Instead, we propose to evaluate patients based on previous fracture history, which is the greatest predictor of future fracture risk ([Banefelt et al, 2019](#); [Balasubramanian et al, 2019](#)).

We propose to have a subgroup analysis of patients with previous bisphosphonate use. Most (64.7%) of patients in the EU had previously used bisphosphonates ([Langdahl et al, 2018](#)). Additional subgroup analyses include evaluation of outcomes by age group and by race/ethnicity.

7.8.11.1. Subgroup Analyses for Effectiveness:

The following subgroup analyses will be performed:

- Age group: < 75 years vs. \geq 75 years
- Race/ethnicity: White, Hispanic, African American, Asian, Other, Unknown, Missing
- Prior use of bisphosphonates within 5 years before the index date: with vs. without
- Prior fracture within 1 year before the index date: with vs. without

Each subgroup will be PS-matched separately to ensure the comparability between the patients in the ABL and TPTD groups.

7.8.11.2. Subgroup Analyses for Safety:

Subgroup analyses will be performed by:

- Age group (age < 75 years vs. age \geq 75 years)
- Race/ethnicity: White, Hispanic, African American, Asian, Other, Unknown, Missing
- With or without prior cardiovascular risk
- With or without MI or stroke within 1 year before the index date.

Each subgroup will be PS-matched separately to ensure the comparability between ABL and TPTD.

7.9. Quality Assurance

Outlined by phase below is PRA Medical Informatics' Codes Review and Quality Control procedure:

1. Pre-Programming Quality Control	In this phase, the Internal Developer will ensure access to all data tables is available, as well as ensure all clinical codes given by the Clinical Lead are aligned with PRA internal standard reference data management tables in the database.
2. Code Quality Control Documentation	In this phase, the Internal Developer will ensure the QC documentation captures each step of the coding process and details all requirements each step is required to implement, the database tables used and/or created as well as the desired outcomes.
3. Code Quality Control Review	In this phase, the Internal Developer and the Peer QC Analyst will walk through the entirety of the code section by section ensuring the code matches the Technical Specifications Document and is producing the desired outcomes. A Quality Gate Acceptance/Failure designation will be assigned at each step in the QC documentation. If a Quality Gate fails at a specific point, the root cause of the failure will be determined (ie, coding errors, problematic business rules, etc.) and appropriate corrective action will be taken. If there has been a coding error, the Internal Developer will correct the error, re-run the code, and produce the requisite outputs. If one or more business rules are causing problems, the business rules may need to be modified. Any business rule modifications will need Project Manager sign-off and be detailed on any documentation going back to the client.

Regardless of the failure, the Quality Control phases will be repeated to ensure the issues have been corrected. (if so, modifications to the business rules may be necessary to match the produced results), or data (if so, additional steps may be required to clean the data as needed to achieve the expected results).

8. PROTECTION OF HUMAN SUBJECTS

The terms of the Research Exception provisions of the Privacy Rule, 45 CFR 164.514(e) exempt Institutional Review Board approval for this non-experimental study, which is fully HIPAA compliant. Data are maintained in a de-identified manner, thus are not subject to institutional review board.

No patients will be directly contacted for participation in the study and no intervention will be provided as part of the protocol. The study will use a secondary data source containing de-identified data.

9. MANAGEMENT AND REPORTING OF ADVERSE EVENTS/ADVERSE REACTIONS

The design of this study is characterized by secondary use of data previously collected from health insurance claims. Thus, for this study the submission of suspected adverse reactions in the form of Individual Case Safety Reports (ICSRs) is not required. The study design was retrospective and there were no claims adjudication. No validated algorithm was used to confirm events were incident events. Claims are therefore only “proxies” for events.

10. PLANS FOR DISSEMINATING AND COMMUNICATING STUDY RESULTS

The study will be registered on ClinicalTrials.gov. The results from this retrospective cohort study evaluating real-world evidence will be submitted as a manuscript to a peer-reviewed journal.

12. APPENDICES

Appendix 1: List of Parameters for Propensity Score Matching

Appendix 2: Fracture Algorithm

A claims-based algorithm with high specificity for fracture site will be used for evaluation of treatment effectiveness ([Wright et al, 2019](#)).

1. All claims with a fracture diagnosis in any position will be evaluated starting 5 years before index to 19 months (18 months plus 30 days follow up, 1 month = 30 days) after index date.
2. Case-qualifying (CQ) fractures are those identified during an inpatient stay or in an outpatient setting accompanied by a fracture repair procedure code on the same day.
3. CQ fracture diagnoses and non-CQ fracture diagnoses will then be used to extend the fracture episode for evaluation of subsequent fractures. Episodes at the same site continued until a gap of 90 days is observed between consecutive claims.

Fracture diagnoses will be based on primary or secondary ICD-9 code before October 2015 or ICD-10 code after that date listed on the same claim.

Appendix 3: Cardiovascular Event Codes

Appendix 4: Diagnostic Codes for All Comorbidities

Sponsor Name: Radius Health, Inc.

Protocol Number: BA058-05-028

Protocol Version and Date: Original, V1.0, dated 09 July 2021

Page 63 of 63

Appendix 5: National Drug Code (NDC) Codes and HCPCS Codes for the Medications Used
